**Primary Exclusion Criteria include but are not limited to:**

Cardiovascular:	myocardial infarction, coronary artery disease, peripheral vascular disease, arrhythmia, congestive heart failure, valvular disease, hypertension
Respiratory:	bronchitis, chronic obstructive pulmonary disease, smoking, shortness of breath
Hepatic:	hepatitis, jaundice, ascites
Neurologic:	seizure, stroke, positive neurologic findings on neurologic examination, multiple sclerosis, Meniere's disease, Parkinson's disease, neuropathy, peripheral stenosis
Gastrointestinal:	esophageal reflux, hiatal hernia, ulcer
Endocrine:	diabetes, thyroid disease
Renal:	acute or chronic severe renal insufficiency
Hematologic:	blood dyscrasias, anemia, coagulopathies, on anticoagulant therapy
Musculoskeletal:	prior surgery or trauma to head neck or face, arthritis, personal or family history of malignant hyperthermia
Psychiatric:	history or treatment for an active psychiatric problem, depression
Reproductive:	pregnancy, breast-feeding
Medications:	regular use of prescription and non-prescription medications expected to affect CNS function, St. John's Wort
Allergies:	labetalol, ondansetron, glycopyrrolate, ketamine, midazolam

**Patients will be excluded from our study if they fail to pass a drug test that screens for the following: Cocaine (COC), d-Amphetamine (AMP), d-Methamphetamine (Mamp), Tetrahydrocannabinol (THC), Methadone (MTD), Opiates (OPI), Phencyclidine (PCP), Barbiturates (BAR), Benzodiazepines (BZO), Oxycodone (OXY)**

**Recruitment:** We will select 15 volunteer subjects (male and female) between the ages of 18-45 years.

The subjects will be recruited using:

An announcement of the study distributed through the Partners Public Affairs distribution list.

The MGH Research Study Volunteer Program (RSVP).

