**4. SUBJECT ENROLLMENT**

**Procedure for informed consent:** Prior to the study, each subject will sign informed consent (detailed in Screening Visit subsection of Study Design Section below). The investigator obtaining consent will explain in detail the protocol of the study, its purpose and potential benefits to society. Subjects will be informed that if they feel uncomfortable with the study, they can choose to terminate the study at any time.

**Treatment Assignment and Randomization:** Not applicable

**Retention:** All subjects who provide verbal or written consent but later decline participation in the study will not be subject to any study-related follow-up.

**Remuneration:** For successful completion of this protocol, subject remuneration will be \$500. The subject will also be compensated for the cost of parking for their study visit.

**Location:** These studies will take place on White 5 at the Carl Rosow Center for Clinical Research. White 5, which is located in the cardiac anesthesia office suite, was constructed specifically for the performance of research on human subjects receiving the depressant medications used in anesthesia. The research area is built to the same standard as a typical surgical procedure room at MGH with respect to ventilation, temperature control, plumbing and electrical facilities, as well as storage. There is piped oxygen and air, wall suction and waste anesthetic gas removal. The hospital's backup generator supports electrical outlets in this location. There is a fully equipped anesthesia machine, standard anesthetic care monitors and a fully equipped code cart. The code cart and medications are checked at intervals by personnel from the OR pharmacy, and the anesthesia equipment is safety checked and maintained by Anesthesia Bioengineering. Research subjects receiving anesthetic drugs in this unit are given an identical standard of care as patients in MGH operating rooms.

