## **6. BIOSTATISTICAL ANALYSIS**

**EEG acquisition Preprocessing:** Continuous 64-channel EEG will be recorded. All data will be stored for subsequent off-line analysis. We will apply an anti-aliasing filter and down-sample the EEG data to reduce computational complexity before analysis. Bandpass filtering of the acquired signal will vary depending upon

the features of the EEG data of interest. Trigger signals will be sent from the stimulus delivery system to the EEG recording system to tag the stimulus events for subsequent binning, temporal epoching and averaging of EEG data into the relevant evoked potential averages.

**Spectral Analysis:** We will compute spectrograms for all subjects using the multitaper method. We will also compute group-level baseline-normalized spectrograms for induction and emergence by taking the median across subjects with the data aligned to the LOC and ROC time points, respectively. To assess statistical significance for the difference in EEG spectra at each frequency, we will compute the 99% confidence interval of the median difference between groups by using an empirical bootstrap approach. The null hypothesis will be rejected only if the confidence interval of the median difference at each frequency exceeds the significance threshold over a contiguous frequency range  $\geq 2W$ .

**Eigenvalue and Modal Projection Analyses:** We will perform an eigenvector decomposition analysis of the cross-spectral matrix to identify the principal modes of oscillation in the conscious and unconscious states and to analyze how activity within these principal modes changes through time. We will estimate the cross-spectral matrices  $P_{\text{baseline}}(f)$  and  $P_{\text{unconscious}}(f)$  at each frequency  $f$  using the multitaper method using data from the full baseline period, as well as segments of at least 5 min extending from LOC to ROC, respectively, for each subject. An eigenvalue decomposition of the median cross-spectral matrix at each frequency will be performed. Each eigenvector describes a coherent spatial distribution or mode of oscillation, and the corresponding eigenvalue quantifies the power in this mode. We then use modal projection analysis to characterize how power within principal modes change as a function of time. A permutation-based procedure will be performed to assess statistical significance for the modal projection analysis.

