**Behavioral Analysis:** The probability of response to verbal stimuli and the difference in probability of response will be estimated by using Bayesian Monte Carlo methods to fit a state-space model to these data. To perform group-level analyses, we will align the behavioral data across subjects with respect to each subject's LOC time for induction and with respect to each subject's ROC time for emergence. We will then pool the responses, and pooled data will be used to estimate group-level probabilities of response using the state-space model.

**Inflammatory profile Analysis:** Plasma samples will be submitted to Myriad/Rules Based Medicine (Myriad RBM, Austin, TX, USA) for analysis using their proprietary platform. Wilcoxon rank-sum tests with corrections for multiple comparisons will be used to assess analyte differences. In exploratory analyses, we will examine Pearson correlations between analytes and variables of interest (i.e. pain, anxiety).

**Power Analysis:** Assuming the point estimate for gamma power at baseline is -20 dB and 5 dB for ketamine induced-unconsciousness (**Fig 2.**), a standard deviation of 20 dB, type 1 error of 0.05, and desired power of 0.9,  $n=14$  study volunteers will enable us to detect a gamma power ratio of 25 dB. Therefore, we aim to recruit up to 15 subjects.

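### The 0.90 power at 14 volunteers is not tied to the only rejection rule stated for spectra, and the plan does not say which SD or which paired test it refers to

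*Combined protocol and SAP*

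**What the plan says.** All of this is in the combined protocol and SAP.

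- **Section 6, Power Analysis.** The inputs are two gamma-power levels ("Assuming the point estimate for gamma power at baseline is -20 dB and 5 dB for ketamine induced-unconsciousness") and "a standard deviation of 20 dB, type 1 error of 0.05, and desired power of 0.9". The conclusion is that 14 "study volunteers will enable us to detect a gamma power ratio of 25 dB", with up to 15 to be recruited. No test is named. The text does not say whether the test is one- or two-sided, or whether 20 dB is the spread of one state or of the change within a person.
- **Section 6, Spectral Analysis.** The plan will compute "group-level baseline-normalized spectrograms for induction and emergence by taking the median across subjects". For significance, "we will compute the 99% confidence interval of the median difference between groups by using an empirical bootstrap approach". Rejection also requires the interval to pass a threshold over an unbroken band at least 2W wide. Neither W nor the threshold is given.
- **Section 6, Eigenvalue and Modal Projection Analyses.** "A permutation-based procedure will be performed to assess statistical significance for the modal projection analysis". No error level is given.
- **Design.** Section 3, Recruitment: "We will select 15 volunteer subjects (male and female) between the ages of 18-45 years". Section 4 marks "Treatment Assignment and Randomization" as not applicable. Section 6 takes baseline and unconscious EEG from each subject.

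**The concern.** There is one group, and each person is measured in two states. The SD that governs power is therefore that of the within-person change, which depends on a correlation the documents do not give. The power statement uses 0.05. The one decision rule written down for spectra uses a 99% interval, a median, and wording that refers to groups, although only one group exists.

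This paragraph is the plan's only justification of the sample size. As written, a reader cannot tell which test has 0.90 power. If the wording about groups were implemented as an unpaired bootstrap, the analysis would also discard whatever precision the repeated measurements offer.

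**Working it through.** **Inputs from Section 6.** Difference 5 − (−20) = 25 dB; SD 20 dB; alpha 0.05, taken as two-sided; power 0.90; n=14, up to 15 recruited. The normal quantiles are 1.960 and 1.282.

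**Step 1: reproduce n=14.**
- Two independent groups, z formula: 2 × (1.960 + 1.282)² × (20/25)² = 13.45, so 14 per group.
- One group, paired z, 20 dB per state, correlation 0: the SD of change is 20√2 = 28.28 dB, and (1.960 + 1.282)² × (28.28/25)² = 13.45, so 14 again.
- One group, paired z, 20 dB as the SD of change: (1.960 + 1.282)² × (20/25)² = 6.72, so 7. A paired t first reaches 0.90 at 9 (0.906).

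The stated n therefore implies 20 dB per state with no gain from pairing. It does not show whether two groups or one uncorrelated pair was intended.

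**Step 2: paired t at the stated 0.05, difference 25 dB.** With correlation ρ, the SD of change is 20√(2(1 − ρ)). Power is from the noncentral t.

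| ρ (assumed) | SD of change (dB) | n=14 | n=15 |
|---|---|---|---|
| 0 | 28.3 | 0.86 | 0.89 |
| 0.3 | 23.7 | 0.95 | 0.97 |
| 0.5 | 20.0 | 0.99 | 0.99 |

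Power reaches 0.90 at ρ of about 0.11 (n=14) or 0.04 (n=15). The row ρ = 0.5 is also the case where 20 dB is itself the SD of change.

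**Step 3: the stated 99% median interval, n=14.** Simulation with normal data, one frequency, rejection when the interval excludes zero, and no 2W condition. The paired runs used 4,000 trials of 2,000 resamples (Monte Carlo error at most 0.008). The plan does not name the interval type, so percentile and basic were both run.

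| ρ (assumed) | Paired by subject: percentile / basic |
|---|---|
| 0 | 0.58 / 0.57 |
| 0.3 | 0.76 / 0.70 |
| 0.5 | 0.90 / 0.81 |
| 0.7 | 0.98 / 0.93 |

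If the two states are resampled independently as though they were separate groups, power is 0.52 to 0.56 at every correlation tried from 0 to 0.75, because the interval does not narrow as the correlation rises.

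**Step 4: error rate of the interval with no true difference.** At one frequency, before 2W and with a zero threshold, the paired interval rejects in about 2% (n=14) to 3% (n=15) of trials for percentile and about 10% to 13% for basic, against a nominal 1%. The powers in Step 3 are not corrected for this.

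**The case against.** The strongest reply is that this is incomplete reporting and not a mistake. The sum is right. A paired z at zero correlation gives the same 14, and the text speaks of 14 volunteers, not 14 per group. So a reader who infers that the wrong two-group formula was used goes beyond the documents. That reply stands.

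Second, 0.05 and 99% need not conflict. The power paragraph concerns gamma power as a single quantity, while the 99% rule works frequency by frequency. A stricter pointwise level with a contiguity condition may serve as multiplicity control for a different analysis. Applying the 20 dB to a single frequency, as Step 3 does, is an assumption. This also stands, but the separate gamma-power test would then have to be named, and it is not.

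Third, the 2% to 13% error rates are not those of the full rule. If two adjacent independent frequencies both had to reject in the same direction, a 12% two-sided rate would fall to about 2 × 0.06² = 0.007. Real multitaper estimates are correlated across frequency, so the true figure is unknown without W. A reader might infer that the spectral test has a 10% false-positive rate; the documents do not support that.

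Finally, Fig 2, cited in the power sentence, was not available for this review and may show which spread is meant. Section 1 describes its data as coming from 12 surgical patients. No hypothesis in Section 2 is worded as this contrast.

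What remains is that no test is named, the SD is unlabelled, and the one rule that is written down has no power statement.

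**Conclusion.** The point holds as a gap in the sample-size justification. The inputs that yield 14 do not give 0.90 under the stated spectral rule: at zero correlation the paired version has about 0.58 and the unpaired version about 0.52. With 20 dB as the SD of change, the paired version has 0.81 to 0.90, and at higher correlation it exceeds 0.90. These figures rest on normal data on the dB scale, a zero threshold, a single frequency, and correlations that the documents do not supply. The effect of the 2W condition is not established.

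It is tempting to conclude that the trial is underpowered. The documents do not support that: under a paired t at the stated 0.05, 14 or 15 volunteers come close to 0.90 at zero correlation and pass it at modest positive correlation. This should be fixed before analysis, but it is no reason to change enrolment.

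**What to change.** Keep 15 volunteers.

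**Spectral Analysis, one sentence.** Replace the reference to groups with the median within-subject difference between baseline and ketamine-induced unconsciousness, resampled by subject. Name the bootstrap interval and state its error rate at 14 to 15 subjects, including W and the threshold.

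**Power Analysis, one paragraph.** Say whether 20 dB is the SD of one state or of the within-subject change, and give its source. Name the paired test and error level that the 0.90 refers to: either a paired test of gamma-band power at 0.05, with its relation to the 99% rule explained, or the 99% rule itself. Restate the power or detectable difference for that test. For example, a paired t at 0.05 with n=15 has 0.90 power for 18.0 dB if the SD of change is 20 dB, or for 25.5 dB if it is 28.3 dB.

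The cost is these two edits and a short recalculation, with no change to enrolment or procedures. Resampling by subject gains power if the two states are positively correlated. The downside is that the stated power may become less favourable.

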## 7. RISKS AND DISCOMFORTS

**EEG risks:** The risks associated with EEG electrodes are redness and irritation at the placement site.

**Questionnaire risks:** Minimal risks associated with completing questionnaires are subject fatigue and the possibility of minor psychological distress associated with answering sensitive questions regarding psychological functioning.

**Data risks:** Procedures are in place to reduce the likelihood of a breach of confidentiality including the de-identification of data and storage of data only on Partners approved devices/portals. However, there is a small risk that people outside of this study may be exposed to information about study subjects.

**Ketamine:** Although it has a good safety profile overall, ketamine has documented sympathomimetic activity that may result in mild to moderate increases in heart rate, blood pressure and cardiac output, though this activity is generally short-lived. Other possible side effects reported during ketamine infusion include arrhythmia, increased salivation, increased bronchial secretions, horizontal nystagmus, euphoria and

hallucinations. Nystagmus may persist for a period after the ketamine infusion has terminated. Any acute changes in physiology, such as changes in heart rate or blood pressure, will be treated using standard anesthesiology practices. Rare side effects are allergic reactions (skin rash), pain at the site of injection, increased intraocular pressure, ulcerations and inflammation in the bladder (reported in ketamine abusers). Ketamine is a controlled substance and has the potential for abuse and dependence, particularly in subjects with history of drug abuse. Subjects with history of substance abuse or dependence will be excluded.

**Glycopyrrolate risks:** Risks involved in the administration of glycopyrrolate include hypertension and tachycardia.

**Labetalol risks:** Risks involved in the administration of labetalol include hypotension and bradycardia.

**Cuff pain stimuli risks:** Risks of cuff pain include mild transient bruising associated with inflation of the cuff. Our previous experience has also demonstrated that pain ratings go down to nil within several seconds of stimulus termination. A button press rapidly deflates the cuff, ensuring subject safety.

**Blood draw risks:** Pain at the needle insertion site, infection, and bleeding.

## **8. POTENTIAL BENEFITS**

Subjects will have no direct benefit from taking part in this study. Ketamine-induced EEG dynamics may aid principled approaches to brain state monitoring and targeting during general anesthesia. They may also lend insights into anti-nociceptive or pain mechanisms.

## **9. MONITORING AND QUALITY ASSURANCE**

The principal investigator and co-investigators will be responsible for monitoring and quality assurance of the study. In conjunction with the research assistants, weekly meetings will be held and documented. Current subjects in the study will be discussed at each meeting, and charts will be reviewed for completeness. The team will evaluate the progress of the study; verify that the rights and well being of the subjects are protected; ensure that the reported study data are accurate, complete and verifiable from source documents; and assure the conduct of the study is in compliance with the approved protocol and amendments.

**Serious Adverse Events:** Expedited review will occur for all events meeting the FDA definition of SAEs – i.e., any events that are fatal, immediately life-threatening, permanently or substantially disabling, or requiring/prolonging inpatient hospitalization. This also includes any event that a study investigator judges to impose a significant hazard, contraindication, side effect or precaution. Reporting to the IRB will be done within 24 hours of the SAE.

**Study Stopping Rules:** If at any time during the course of the study the PIs or CO-Is judge that risk to subjects outweighs the potential benefits, the PI/CO-Is shall have the discretion and responsibility to recommend that the study terminated.

**AE Reporting Guidelines:** Unanticipated problems involving risks to subjects or others including adverse events will be reported to the PHRC in accordance with PHRC unanticipated problems including adverse events reporting guidelines, as well as the RDRC within 5 days.

